## 1.0 Objectives

### 1.1 Study Objectives

Hypothesis: Patients on Angiotensin Converting Enzyme Inhibitors (ACEI) or Angiotensin Receptor Blockers (ARB) experience more profound hypotension upon anesthetic induction with propofol compared with methohexitol.

Specific Aim 1: To determine the incidence of hypotension during anesthetic induction with propofol and methohexitol in patients being chronically treated with ACEI or ARB.

Specific Aim 2: To determine the effect of propofol and methohexitol on circulating neurohormones relevant to hemodynamic homeostasis in this population, namely arginine vasopressin (AVP), Angiotensin II (All), norepinephrine (NE) and epinephrine (Epi).

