#### **7.4.3 Method for Assigning Subject to Treatment Groups**

The randomization scheme for this study will use variable-size, random permuted blocks to ensure that the number of participants in each treatment arm is balanced after each set of  $B$  randomized participants, where  $B$  is the block size. We will use a block size of 10. Furthermore, the randomization will be stratified by gender (male/female) and drug type (ACEI/ARB). Randomization to the propofol or methohexitol arms will use 1:1 allocation. A research coordinator will access the randomization lists (developed through the website Randomization.com) stored in the secure REDCap database to randomize the participant.

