## 8.3 Statistical methods

Primary analyses will invoke an intent-to-treat paradigm, wherein all randomized subjects are included according to their randomized treatment arm, regardless of actual treatment received, compliance, etc. Data will be summarized using descriptive statistics for continuous variables (mean, standard deviation, number of observations, and percentiles) and frequency statistics (frequencies and percentages) for categorical variables. Univariate and bivariate distributions will be inspected in order to address any missing data, inconsistent responses, outliers, and data entry errors. The sample size estimates have taken into consideration a participant drop-out of 20%; however, every effort will be made during the studies to minimize any drop-out. All hypothesis tests will be two-sided and analyses will account for the two randomization stratification factors of gender and inhibitor type. All analyses will be performed using SAS software, version 9.4 (SAS Institute, Inc., Cary, NC), R software, version 3.2.2 (R Foundation for Statistical Computing, Vienna, Austria), or Stata software, version 13 (StataCorp LP, College Station, TX).

For the primary outcome of the proportion of participants having at least one hypotension episode, log-binomial regression will be used to compare the propofol and methohexitol groups, adjusting for the randomization stratification factors of gender and inhibitor type. Because this is a prospective study, the log-binomial model allows us to estimate the risk ratio rather than the odds ratio while adjusting for covariates (Wacholder, 1986).

For secondary outcome of the proportion of patients experiencing refractory hypotension, the log-binomial model as described for the primary outcome will be used to compare the treatment groups. Poisson regression will be used to compare the two treatment groups, adjusting for the randomization stratification factors, with respect to the secondary outcomes of (a) the number of vasopressor doses (i.e., ephedrine, phenylephrine and vasopressin) administered per patient and (b) the number of hypotension episodes per patient over the first 18 after treatment initiation. In the event that there is an excess of zero counts, zero-inflated Poisson (ZIP) regression will be considered (Lambert, 1992).

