For secondary hemodynamic outcomes of systolic blood pressure, diastolic blood pressure and heart rate over the first 15 minutes after treatment initiation, the area under the curve (AUC) for each of these variables will be calculated using the trapezoidal rule. The AUC of each of these variables will be compared between the two treatment groups using linear regression models adjusting for the randomization stratification factors. A linear regression model also will be used to assess differences between the two treatment groups with respect to the duration (in minutes) of hypotension.

Blood will be collected at baseline, 3 min, 5 min, 10 min, and 15 min after treatment initiation to assess changes from baseline in AVP, AI, Epi and NE between the two treatment groups. For these continuous secondary outcomes collected longitudinally, linear mixed-effects models will be fit to compare the two treatment arms with respect to changes in these outcomes over time(Laird and Ware, 1982). The independent variables in the model will be treatment arm, time, the interaction of treatment and time, as well as the randomization stratification factors as covariates. From the mixed-effects models, contrasts will be constructed to test the hypotheses of interest with respect to changes over time in the outcomes. Linear mixed-effects models are an extension of ordinary regression models that account for the between- and within-subject correlation inherent in data involving repeated measurements per subject and allows for the variance-covariance matrix to be explicitly defined.

Following our assessment of the initial fit of the models, we will add covariates to the models that correspond to potential confounders to assess their impact, if any, on the treatment effects. Residual diagnostics will be assessed to determine the appropriateness of the model fit and, if necessary, transformations of the response will be used to meet modeling assumptions. Differences in means and associated confidence intervals (CIs) will be used to quantify the magnitude of the effects for continuous outcomes.

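### The neurohormone model enters gender and inhibitor type only as main effects, which cancel from the change-over-time contrasts, so those contrasts are in effect unadjusted and their reported standard errors may be too large

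*Combined protocol and SAP*

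**What the plan says.** Section 8.3 of the combined protocol and SAP makes a general commitment: "analyses will account for the two randomization stratification factors of gender and inhibitor type". Section 7.4.3 stratifies the randomization by these two factors, with 1:1 allocation and a block size of 10.

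For the hormones, section 8.3 states the purpose of sampling: "Blood will be collected at baseline, 3 min, 5 min, 10 min, and 15 min after treatment initiation to assess changes from baseline". The fixed effects of the linear mixed model are arm, time, "the interaction of treatment and time, as well as the randomization stratification factors as covariates". No product of a stratum with time is listed. Inference comes from the fitted model: "contrasts will be constructed to test the hypotheses of interest with respect to changes over time in the outcomes".

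Three things are left open. The response is not named (raw level or change from baseline), the covariance structure is not named, and the response may be transformed. A later step allows further adjustment: "we will add covariates to the models that correspond to potential confounders to assess their impact, if any, on the treatment effects". No interaction of such covariates with time is mentioned.

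**The concern.** A main effect for inhibitor type or gender moves a patient's whole profile up or down by the same amount at every time. The hormone hypotheses are about how the arms differ in change, and a constant shift has no effect on a change. The stratum terms would therefore be in the model, meeting the letter of the general commitment, without adjusting the quantity that is tested.

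Two things are at stake for these secondary outcomes. If patients on the two inhibitor types (or men and women) change by different amounts, that difference stays in the residual variation and widens the confidence intervals. And if the strata become unbalanced between arms after removals or drop-out, the main effect cannot correct for it. The same holds for any time-fixed confounder added later as a main effect. With complete data it leaves the change contrasts as they were, so the planned check of its impact would show none whatever the truth.

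**Working it through.** **Plan's own figures.** The documents give no SD, effect size or sample size for the hormones and no ACEI/ARB split. The only sample size is for the primary endpoint (section 8.1): 47 per group, 90% power, difference 0.30, two-sided 0.05. With an assumed 0.85 versus 0.55 (section 8.2 expects slightly more than 0.82 on propofol), the pooled-variance formula gives 46.9, so 47 per group. That agrees with the plan. The check below uses 2 x 47 = 94 patients.

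**Step 1: cancellation.** Write the level for a patient with arm indicator A and stratum indicator S at time t as

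Y(t) = m(t) + A·b(t) + S·g + e(t).

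The change from baseline is

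Y(t) − Y(0) = [m(t) − m(0)] + A·[b(t) − b(0)] + [e(t) − e(0)].

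The term S·g has gone. This does not require balanced strata. It does require the raw level as response and complete data; with missing samples the cancellation is only approximate. In simulated data (94 patients, five times, within-patient correlation 0.5, stratified blocks of 10), the 15-minute change contrast with strata as main effects equalled the contrast with no strata. The largest difference was about 1e-14, under both unstructured and compound-symmetry covariance.

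**Step 2: reported standard error.** Let p be the ACEI share and d the ACEI–ARB difference in mean change, in within-class SDs of change. The model leaves that difference in the residual, so for unstructured covariance

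reported SE / SE with inhibitor x time = sqrt(1 + p(1 − p)d²).

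The values of d and p are assumptions, shown over a range.

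| d | p = 0.5 | p = 0.7 |
|---|---|---|
| 0 | 1.00 | 1.00 |
| 0.5 | sqrt(1.0625) = 1.03 | sqrt(1.0525) = 1.03 |
| 1.0 | sqrt(1.25) = 1.12 | sqrt(1.21) = 1.10 |
| 1.5 | sqrt(1.5625) = 1.25 | sqrt(1.4725) = 1.21 |

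Simulated mean reported SEs at p = 0.5, main effects versus interaction added (300 replicates per setting):
- d = 0: 0.207 vs 0.206
- d = 0.5: 0.212 vs 0.204
- d = 1.0: 0.231 vs 0.204
- d = 1.5: 0.258 vs 0.205

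The simulated ratios lie within about 0.015 of the formula. Under compound symmetry the excess at d = 1.0 is smaller: 0.215 vs 0.206, about 4%.

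**Step 3: true variability.** The empirical SD of the arm estimate hardly moved when the interaction was added: 0.204 vs 0.205 at d = 1.0, and 0.220 vs 0.216 at d = 1.5. With 300 replicates an empirical SD is uncertain by about 1/sqrt(600) = 4%, so these are equal within simulation error. No bias was seen. The stratified blocks already balance the arms; what is wrong is the reported error.

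**Step 4: what that does to a test.** With true variability unchanged and a nominal two-sided 5% level (assumed for the hormone tests), the actual level at p = 0.5 is about 2[1 − Φ(1.96 x ratio)]: 4.3% at d = 0.5, 2.8% at d = 1.0 and 1.4% at d = 1.5. The test is conservative.

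**Step 5: imbalance.** In one illustrative dataset of 94 patients with no true arm effect, the stratum share was deliberately set far apart (25% vs 63% by arm) and the strata differed by 1 SD in change. The arm-by-time estimate was 0.4625 without the stratum, 0.4625 with its main effect, and −0.041 with stratum x time. This is an extreme case, used only to show that the main effect corrects nothing.

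**The case against.** The strongest reply is that nothing is broken. The strata are in the model as covariates, which is the usual way of accounting for them, and the randomization is stratified on them. The estimate is unbiased, its real variability is almost the same, and any error is conservative. This stands, and it limits the point to the size of the reported error and to protection against later imbalance.

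Second, the cancellation depends on the response. If change from baseline at the four post-dose times were modelled, a stratum main effect would not drop out of the arm difference at each time. This also stands as a possible reading. But the text lists baseline among the sampling times and tests changes over time by contrasts from the model, which points to raw levels. The plan should settle it.

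Third, the loss needs a stratum difference in change on the analysed scale. A difference in level alone costs nothing, and a transformation could remove a proportional difference. This stands; the percentages are conditional.

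A reader might go further and infer from the class names ("Patients on Angiotensin Converting Enzyme Inhibitors (ACEI) or Angiotensin Receptor Blockers (ARB" in section 1.1) that angiotensin II is a different readout under the two inhibitor types, so that the pooled contrast hides class-specific or opposite effects. The documents do not say this. The background and rationale treat both classes together as antagonists of the renin-angiotensin system, and no cited figure shows that the propofol–methohexital difference depends on class. That question would in any case need an arm x time x inhibitor term, which is separate from the adjustment discussed here.

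**Conclusion.** The point holds in a limited form. With raw levels as response and complete data, the hormone change contrasts in section 8.3 are in effect unadjusted for gender and inhibitor type. If the strata differ in mean change, the reported SE is too large: by 0%, 3%, 12% and 25% at assumed differences of 0, 0.5, 1.0 and 1.5 SD of change (50:50 split, unstructured covariance), and by about 4% at 1.0 SD under compound symmetry. Intervals are then too wide and tests conservative. The main effect also gives no protection against stratum imbalance arising from the removals in sections 3.3.1, 7.2.2 and 19.7 or from the drop-out of up to 20% foreseen in section 8.1.

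A reader might conclude that stratification buys these outcomes no precision, or convert the SE excess into patients lost. Neither follows. The stratified blocks already deliver the balance, and the estimator's true variability is almost unchanged; only its reported error fails to reflect the design.

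These are secondary outcomes. The primary analysis and the sample size are unaffected.

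**What to change.** In section 8.3, name the response and the covariance structure for the hormone models, and then do one of the following for AVP, angiotensin II, epinephrine and norepinephrine:

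- keep the raw level at all five times and add inhibitor type x time and gender x time; or
- model change from baseline at the four post-dose times, with the baseline value and the strata as covariates.

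Treat any confounder added later in the same way: under the raw-level model it needs its own product with time.

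Arm contrasts for angiotensin II within the ACEI and ARB strata may be reported as well, labelled descriptive.

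The change is to SAP wording only. With five times, each stratum x time term uses 4 degrees of freedom, so the cost is 4 for one factor and 8 for both. If the strata do not differ in change there is no gain in the reported SE.

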applied to the ipsilateral arm. An appropriately-sized blood pressure cuff shall be defined as a cuff whose bladder length is at least 80% of the arm circumference, and whose width covers 2/3 of the distance from the elbow to the shoulder. Blood samples, for baseline analysis of AVP, All, NE and Epi levels, will be collected from the IV as follows: A tourniquet will be applied proximal to the intravenous catheter, following which 3cc of blood will be removed first to clear the 'dead space' in the intravenous line and prevent erroneous blood sampling. This blood will be discarded. A further 10cc of blood will be collected in appropriately labeled tubes (5ml in serum red top vacutainers tubes and 5ml in vacutainers tubes containing EDTA) and kept on ice until processing by our research technician, as described below. Following collection of the blood sample, 5cc of normal saline will be used to flush the line and prevent blood from clotting the catheter. A second IV will also be established in the preoperative area under local anesthesia as described above to administer intravenous medications and fluids intraoperatively according to current anesthetic standards of care.

**Operating Room Procedures:** Subjects will be attached to standard ASA monitors including electrocardiogram and pulse oximetry and noninvasive blood pressure monitor. Baseline blood pressure will be determined by taking three automated successive non-invasive blood pressure measurements every 1-2 minutes, until the systolic blood pressure (SBP) measurements is consistent (difference of no more than 10% between readings) with the patient lying in supine position. The average SBP and accompanying heart rate (HR) of these three measurements will be recorded as mean baseline values.

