### **8.0      Subject Numbers and Statistical Plan**

#### **8.1      Number of Subjects**

The total sample size will consist of 120 participants (i.e., 60 per treatment arm). A sample size of 47 subjects per group will provide 90% statistical power to detect a difference of 0.3, between the proportion of subjects having at least one hypotension episode in the propofol group compared to the proportion in the methohexitol group, using a two-sided, chi-square test having a significance level of 0.05. However, we anticipate a drop-out rate as high as 20% for this study; therefore, we will enroll a total of 120 subjects.

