## 8.2 Sample size determination

The primary outcome of this two-arm trial is the proportion of subjects that have at least one hypotension episode within 15 minutes of administration of the randomized treatment medication. A hypotension episode is defined as having a drop in systolic blood pressure  $>30\%$  from baseline and/or having systolic blood pressure  $<85$  mmHg. Eyraud et al found 42 out of 51 subjects (0.82) had at least one hypotension episode using propofol (Eyraud et al., 1999). We expect our propofol proportion to be slightly higher due to our definition of a hypotension episode and our patient population. Further, we believe an absolute reduction of 0.30 in the proportion of subjects having at least one hypotension episode in the methohexitol group compared to the propofol group is clinically important. Although the randomization will be stratified by two factors (gender and drug type), to provide a conservative sample size estimate these factors were not taken into consideration for the power analysis because the correlation of these stratification covariates with the outcome would simply increase the precision, and hence, increase the power.

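### The secondary SBP, DBP and HR AUC models leave out the patient's own baseline value and so give up precision that data largely in hand could supply

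*Combined protocol and SAP*

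**What the plan says.** Section 1.3 lists SBP, DBP and HR at one-minute intervals over the first 15 minutes as secondary endpoints. Section 8.3 reduces each to an AUC by the trapezoidal rule and compares the arms "using linear regression models adjusting for the randomization stratification factors". Those factors are gender and ACEI versus ARB (section 7.4.3). No baseline term is listed.

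Baseline is nevertheless measured. Under the operating room procedures in section 7.2.2, three supine cuff readings are taken before induction, and "The average SBP and accompanying heart rate (HR) of these three measurements will be recorded as mean baseline values". Baseline DBP is not named there.

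After describing all the models, section 8.3 adds that, once the initial fit has been assessed, "we will add covariates to the models that correspond to potential confounders to assess their impact, if any, on the treatment effects". It lists no covariates, and it does not say which model carries the inference once they have been added.

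**The concern.** A patient who starts with a higher pressure or heart rate will tend to have a higher raw AUC whichever drug is given. With no baseline term, that between-patient variation stays in the residual and widens the confidence interval for the treatment difference. The plan accepts the principle elsewhere. Section 8.2 argues that covariates related to the outcome raise precision and power, the neurohormone analysis is framed as change from baseline, and the primary endpoint is defined partly relative to baseline SBP. The haemodynamic AUCs are the exception.

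At stake is the width of the intervals on three secondary outcomes. A smaller matter goes with it. The later covariate models have no stated status, so a report could leave unclear which estimate is the planned one.

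**Working it through.** **1. The plan's own figure.** Section 8.1 states: "A sample size of 47 subjects per group will provide 90% statistical power to detect a difference of 0.3", "using a two-sided, chi-square test having a significance level of 0.05". Section 8.2 cites "42 out of 51 subjects (0.82) had at least one hypotension episode using propofol" and expects a slightly higher rate, without giving one. I assume 0.85 versus 0.55, so the pooled proportion is 0.70:

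n = [1.96 × √(2 × 0.70 × 0.30) + 1.2816 × √(0.85 × 0.15 + 0.55 × 0.45)]² / 0.30² = (1.270 + 0.785)² / 0.09 ≈ 46.9, so 47 per group.

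With 20% drop-out, 47 / 0.8 = 58.75, so 59 per arm or 118 in total, which the plan rounds to 120. At 0.82 versus 0.52 the formula gives 50 per group, and 47 per group then has power 0.884. The stated size therefore reproduces. It is an unadjusted calculation for the binary primary outcome, so the AUC models play no part in it.

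**2. Gain from a baseline term.** Inputs: N = 120 enrolled, or 94 (2 × 47) at the planned analysis size; ρ is the within-arm correlation between baseline and AUC. The documents give neither ρ nor the SD of any AUC, so ρ is assumed and effects are in SD units.

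- Residual variance after adjustment = 1 − ρ² of the unadjusted value
- Confidence interval width ratio = √(1 − ρ²)
- Equivalent unadjusted sample size = N / (1 − ρ²)

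| ρ (assumed) | Variance removed | CI width ratio | Sample size factor | Equivalent of N = 94 | Equivalent of N = 120 |
|---|---|---|---|---|---|
| 0.3 | 9% | 0.954 | 1/0.91 = 1.10 | 103 | 132 |
| 0.5 | 25% | 0.866 | 1/0.75 = 1.33 | 125 | 160 |
| 0.7 | 49% | 0.714 | 1/0.51 = 1.96 | 184 | 235 |

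**3. The same gain as power.** For an illustrative difference of 0.5 SD, two-sided 0.05, with n per arm, power = Φ(0.5 × √(n/2) / √(1 − ρ²) − 1.96).

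- N = 120: unadjusted, 0.5 × √30 = 2.739 and Φ(0.779) = 0.78. Adjusted: 0.82, 0.89 and 0.97 at ρ = 0.3, 0.5 and 0.7.
- N = 94: unadjusted, 0.5 × √23.5 = 2.424 and Φ(0.464) = 0.68. Adjusted: 0.72, 0.80 and 0.92.

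**4. Does the AUC already contain baseline?** The plan does not say whether a time-zero value enters the trapezoidal sum. If it did, with one-minute spacing it would carry half an interval out of 15, or 0.5/15 = 3.3% of the weight. That would not replace adjustment.

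**The case against.** The best defence is that nothing here is an error. In a randomised comparison, omitting baseline leaves the estimate unbiased, and the unadjusted standard error already allows for chance imbalance. The AUCs are secondary and no power claim rests on them. All of that stands: this is lost efficiency, not invalidity.

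The size of the gain is also open. Section 7.2.2 has SBP below 85 mmHg treated with vasopressors within the same 15 minutes, and section 8.2 expects more than 0.82 of propofol patients to meet the hypotension definition, which also counts drops above 30%. Treating low readings may loosen the link between baseline and AUC, so the figures at ρ = 0.7 may be too generous.

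Three stronger readings are tempting and should not be drawn.

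- A reader might infer that an open-label team will pick covariates to suit the result. Simulating that worst case (smallest p-value over all subsets of candidate covariates that explain 10% to 50% of the variance) gives a type I error of 0.07 to 0.14 with three candidates and 0.09 to 0.19 with five. The plan describes no such procedure. Its initial models are fixed in advance, and the later covariates are there to assess impact, which reads naturally as a sensitivity check. What remains is a missing label.
- A reader might take the 180 mmHg limit in section 3.2 as evidence that baseline SBP varies widely. That limit applies at the preoperative clinic visit, not to the supine operating-room baseline, and an upper limit says nothing about spread.
- A reader might assume that all three baselines are already recorded. Section 7.2.2 names only SBP and HR.

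**Conclusion.** The point holds as a precision improvement for three secondary outcomes. The AUC models omit the covariate most likely to predict each outcome, and for SBP and HR that covariate is already being recorded. For assumed correlations of 0.3 to 0.7 the avoidable loss is 9% to 49% of residual variance. Any non-zero correlation gives some gain, apart from the negligible cost of one degree of freedom; how much depends on a value the documents do not supply.

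The primary log-binomial analysis, the sample size of 120 and the validity of the randomised comparison are unaffected. The neurohormone mixed models do not share the omission in the same way, because they use a baseline sample and assess change from it. The status of the later covariate models is a gap in wording only.

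**What to change.** In section 8.3, give each haemodynamic AUC model terms for treatment arm, gender, inhibitor type and the pre-induction mean of the same variable: baseline SBP for the SBP AUC, baseline HR for the HR AUC, and baseline DBP for the DBP AUC. Name this as the reported model for each outcome.

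In section 7.2.2 and on the data collection sheet, add mean DBP from the same three readings to the recorded baseline values.

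At the end of section 8.3, state that any covariate models fitted after the initial fit has been assessed are sensitivity analyses and do not replace the pre-specified models, for the primary and the secondary outcomes alike.

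The cost is one extra term in three models, one more recorded value per patient and a few lines of text. No new measurement or additional patient is needed.
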